3.1.2 Exclusion Criteria

Participants who exhibit any of the following conditions will not be eligible for admission into the study:

3.1.2.1 Prior immunotherapy except for anti-CTLA-4. Patients with unresectable melanoma who have received PD-1 inhibition therapy as adjuvant therapy and stopped receiving PD-1 inhibition for a period of \geq 6 months before starting treatment with Nivolumab are allowed to participate.

3.1.2.2 > 24 weeks between surgical resection of stage IIIB/C/D or IV melanoma and initiation of study treatment

3.1.2.3 Concomitant therapy with any anti-cancer agents, other investigational anti-cancer therapies, or immunosuppressive agents including but not limited to methotrexate, chloroquine, azathioprine, etc. within six months of study participation

3.1.2.4 Active brain metastases or leptomeningeal metastases

3.1.2.5 Use of a non-oncology vaccine therapy for prevention of infectious diseases (with the exception of vaccination against the SARS-CoV-2 virus for the prevention of COVID-19 disease) during the 4 week period prior to first dose of Nivolumab. Participants may not receive any non-oncology vaccine therapy during the period of Nivolumab or NeoVax plus Montanide administration and until at least 8 weeks after the last dose of study therapy.

Given the severity of the COVID-19 pandemic, vaccination specifically against the SARS-CoV-2 virus for the prevention of COVID-19 is ALLOWED in this study.

3.1.2.6 History of severe allergic reactions attributed to any vaccine therapy for the prevention of infectious diseases.

3.1.2.7 Active, known or suspected autoimmune disease. Subjects are permitted to enroll if they have vitiligo, type I diabetes mellitus, residual hypothyroidism due to autoimmune condition only requiring hormone replacement, psoriasis not requiring systemic treatment, or conditions not expected to recur in the absence of an external trigger.

3.1.2.8 A condition requiring systemic treatment with either corticosteroids (> 10 mg daily prednisone equivalents) or other immunosuppressive medications within 14 days of study drug administration. Inhaled or topical steroids and adrenal replacement doses > 10 mg daily prednisone equivalents are permitted in the absence of active autoimmune disease. Corticosteroids used as pre-medication for imaging studies are allowed.

3.1.2.9 Test positive for hepatitis B virus surface antigen (HBV sAg) or hepatitis C virus ribonucleic acid (HCV antibody) indicating acute or chronic infection.

3.1.2.10 Known history of testing positive for human immunodeficiency virus (HIV) or known acquired immunodeficiency syndrome (AIDS).

3.1.2.11 Known sensitivity or allergy to Nivolumab and/or Ipilimumab.

3.1.2.12 Uncontrolled intercurrent illness including, but not limited to ongoing or active infection requiring treatment, symptomatic.

3.1.2.13 Any underlying medical condition, psychiatric condition or social situation that in the opinion of the investigator would compromise study administration as per protocol or compromise the assessment of AEs.

3.1.2.14 Planned major surgery (excluding surgery for resection of melanoma if applicable).

3.1.2.15 Pregnant women are excluded from this study because Nivolumab, personalized neoantigen peptides and poly-ICLC are agents with unknown risks to the developing fetus. Because there is an unknown but potential risk of adverse events in nursing infants secondary to treatment of the mother with Nivolumab, personalized neoantigen peptides and poly-ICLC, nursing women are excluded from this study.

3.1.2.16 Individuals with a history of an invasive malignancy are ineligible except for the following circumstances: a) individuals with a history of invasive malignancy are eligible if they have been disease-free for at least 3 years and are deemed by the investigator to be at low risk for recurrence of that malignancy; b) individuals with the following cancers are eligible if diagnosed and treated - carcinoma *in situ* of the breast, oral cavity or cervix, localized prostate cancer, basal cell or squamous cell carcinoma of the skin.

3.1.2.17 Prisoners, or subjects who are compulsory detained are not eligible to participate.

3.2 Inclusion of Women and Minorities

Both men and women of all races and ethnic groups are eligible for this trial.

4. REGISTRATION PROCEDURES

Eligibility will be confirmed prior to the initial biopsy to obtain tumor for sequencing. Prior to initial biopsy, the patient is screened for eligibility using the eligibility checklist. Once overall trial initial eligibility is confirmed, the patient is registered, undergoes core needle or surgical biopsy and preparation of the participant's vaccine is initiated (while the patient is receiving Nivolumab).

Before the first dose of the vaccine plus ipilimumab the patient will be registered to the correspondent dose level vaccine plus ipilimumab.

4.1 General Guidelines for DF/HCC Institutions

Institutions will register eligible participants in the Clinical Trials Management System (CTMS) OnCore. Registrations must occur prior to the initiation of protocol therapy. Any participant not registered to the protocol before protocol therapy begins will be considered ineligible and registration will be denied.

For registration, an investigator will confirm eligibility criteria and a member of the study team will complete the appropriate protocol-specific eligibility checklist.

Following registration, participants may begin protocol therapy. Issues that would cause treatment delays should be discussed with the Overall Principal Investigator (PI). If a participant does not receive protocol therapy following registration, the participant's registration on the study must be canceled. Registration cancellations must be made in OnCore as soon as possible.

4.2 Registration Process for DF/HCC Institutions

The Registration procedures are as follows:

To be eligible for registration to the study, the participant must meet each inclusion and exclusion criteria listed in protocol section 3.

Reminder: Confirm eligibility for ancillary studies at the same time as eligibility for the treatment study. Registration to both treatment and ancillary studies will not be completed if eligibility requirements are not met for all studies.

1. Confirm written informed consent from the participant has been obtained prior to the performance of any protocol-specific screening procedures or assessments.
2. Complete the *Eligibility Checklist*
3. Perform subject registration per DF/HCC SOP REGIST-101
4. Verify the success of the subject registration in all DF/HCC systems.

5. TREATMENT PLAN

Overall Treatment administration

Treatment will be administered on an outpatient basis. Expected toxicities and potential risks as well as dose modifications for Nivolumab and NeoVax plus Montanide and locally administered Ipilimumab, respectively, are described in Section 6 (Expected Toxicities and Dosing Delays/Dose Modification). No investigational or commercial agents or therapies other than those described below may be administered with the intent to treat the patient's malignancy.

Participants will be identified and enrolled on the study if they meet all eligibility criteria. After confirmation of adequate tumor content in the surgical resection/core biopsy specimen (at least 30% tumor in specimen), each participant will start receiving Nivolumab as described in section Section 5.2.1, while vaccine is being prepared. If there is no adequate tumor content in the specimen, the patient will be removed from protocol and replaced. Treatment with NeoVax plus Montanide plus local Ipilimumab will begin within 12 weeks after initiation of Nivolumab. Days will not be counted continuously on protocol therapy. If a toxicity results in a hold of study vaccine administration, counting of days will hold until treatment resumes (e.g. should a patient not be able to receive his/her second vaccine at Week 15 due to a toxicity, counting is held; if the toxicity has resolved a week later, the administration of that second vaccine becomes the participant's new Week 15). Following a dose delay, those day's assessments should be repeated in order to restart participant's vaccinations.

5.1 Preparation of NeoVax plus Montanide

5.1.1 Tumor and normal tissue harvest

Patients with resectable or unresectable melanoma will undergo surgical resection, surgical biopsy, or core needle biopsy of a melanoma metastasis. For patients with melanoma that has already been completely resected, archival tissue can be used for assessment of tumor content by a staff pathologist at Brigham and Women's Hospital (in an H&E stained tumor specimen) as well as whole-exome and transcriptome sequencing. [name], the principal investigator (██████████) should be contacted at the time of the initial consent to ensure that ancillary studies are coordinated.

For patients with resectable or unresectable melanoma who undergo surgical resection, surgical biopsy, or core needle biopsy of a melanoma metastasis, the study investigators and members of the study team will coordinate tissue acquisition with the interventional radiology or surgical staff of the Brigham and Women's Hospital and the staff of the BWH-SHL, and TIGL. After adequate tumor for pathological assessment has been harvested as deemed by the interventional radiologist or surgeon, some or all of the remaining tumor tissue will be placed in sterile media in a sterile container and transferred to the Specialized Histopathology Core at BWH. A staff pathologist at Brigham and Women's Hospital will assess H&E stained tumor specimen for tumor content. Portions of the tumor tissue will be used for whole-exome and transcriptome sequencing. Cell line and tumor infiltrating lymphocyte generation (if adequate tissue) will be performed in the Translational Immunogenomics Laboratory (TIGL).

In the event that sequence analysis yields no results or sub-optimal results, tumor cell line cells or paraffin embedded tumor sections from the recently resected tumor (if available) may be used to prepare additional nucleic acid for sequencing. No saved samples will be used to prepare cellular products for future clinical use. Peripheral blood mononuclear cells from a blood draw will be utilized for a normal tissue sample.

5.1.2 DNA/RNA Sequencing

Nucleic acid will be extracted from the tissue samples and sequencing will be conducted at either the CLIA-certified laboratory at Broad Institute/Clinical Research Sequencing Platform (CRSP) ██████████. Samples will be de-identified before being shipped to either the Clinical Research Sequencing Platform (CRSP) and Broad Genomics Platform research lab at the Broad Institute ██████████.

Sequencing at the Broad Institute

Whole-exome sequencing will be conducted in the Clinical Research Sequencing Platform, LLC (CRSP) at the Broad Institute. CRSP is CLIA licensed (██████████) and CAP accredited ██████████ and one of tests offered by CRSP is Somatic Whole Exome sequencing, which will be utilized for these trials. CRSP will extract total DNA from blood and tumor tissue using standardized procedures. The DNA samples will be processed through the CLIA Somatic WES test. For tumor and normal DNA samples, whole exome capture will be conducted prior to sequencing on Illumina HiSeq or NovaSeq. RNA sequencing is completed at the non-CLIA Broad Genomics Platform research lab. For tumor RNA, a cDNA library will be prepared and

may be enriched by transcriptome capture prior to sequencing on Illumina HiSeq or NovaSeq. If the quantity or quality of DNA or RNA isolated from the tissue sample is inadequate for exome or cDNA library preparation and sequencing, then DNA or RNA may be extracted from the patient-specific tumor cell line (if generated).

5.1.3 Preparation of personalized neoantigen peptides

[REDACTED]

[REDACTED]

[REDACTED]

|| [REDACTED]

[REDACTED]

[REDACTED]

[REDACTED]

[REDACTED]

[REDACTED]

[REDACTED]

5.1.3.1 Peptide synthesis

[REDACTED]

5.1.3.2 Preparation of Neoantigen peptide pools

[REDACTED]

[REDACTED]

5.2 Agent Administration

Agent	Treatment phase	Schedule**	Allowable Treatment Admin Window	Dose	Route
Nivolumab	Entire Duration	Every 4 weeks	± 3 days	480 mg flat dose	i.v.
Neoantigen Vaccine (peptides + poly-ICLC + Montanide® ISA-51 VG)*.***	Vaccination Phase	Week 12, 15, 18, and 21	± 3 days	
Poly-ICLC: 2 x 0.5 mg (0.25ml each)
 
Peptides: 2 x 300μg per peptide/0.75ml
 
Montanide® ISA-51 VG: 2 x 1ml
 
Total Neoantigen Vaccine Volume*: up to 2 x 1.6 ml
	Neoantigen Vaccine s.c. injections into up to 2 different anatomic sites
Ipilimumab	Vaccination Phase	Week 12, 15, 18, and 21	± 3 days	2 x 1.25 mg (0.25ml), 2.5 mg (0.5 ml) or 5 mg (1.0 ml) depending on the cohort	s.c injection within 1 cm of each Neoantigen Vaccine injection

*During NeoVax (personalized neoantigen peptides + Hiltonol) and Montanide mixing preparation there is a loss of 0.4 mL

**Please refer to section 5.2.1.2 regarding delays on vaccination therapy start

***If emulsion of either pool A or pool B or both pools A and B is unsuccessful after two attempts, the neoantigen vaccine will be prepared without Montanide as stated in section 8.6.3.

If one of the initial vaccine doses is not successfully emulsified with montanide after two attempts, the vaccine will be prepared without the Montanide (see table below and section 8.6.3).

During the vaccination treatment period if any of the two vaccine doses is not successfully emulsified with montanide after two attempts, the vaccine will be prepared without the Montanide.

Treatment plan if emulsion NeoVax – Montanide fails:

Agent	Treatment phase	Schedule**	Allowable Treatment Admin Window	Dose	Route
Nivolumab	Entire Duration	Every 4 weeks	\pm 3 days	480 mg flat dose	i.v.
NeoVax (peptides + poly-ICLC)***	Vaccination Phase	Week 12, 15, 18, and 21	\pm 3 days	
Poly-ICLC: 2 x 0.5 mg (0.25ml each)
 
Peptides: 2 x 300μg per peptide/0.75ml
 
Total NeoVax Volume: up to 1.0 ml (+/- 0.1 ml)
	NeoVax s.c. injections into up to 2 different anatomic sites
Ipilimumab	Vaccination Phase	Week 12, 15, 18, and 21	\pm 3 days	2 x 1.25 mg (0.25ml), 2.5 mg (0.5 ml) or 5 mg (1.0 ml) depending on the cohort	s.c injection within 1 cm of each NeoVax injection

***If emulsion of either pool A or pool B or both pools A and B is unsuccessful after two attempts the vaccine will be prepared without Montanide as stated in section 8.6.3

5.2.1 Nivolumab

5.2.1.1 Nivolumab Run-in Period

Run in period will begin within 2 weeks of metastatic tissue biopsy or within 4 weeks of enrollment if the patient has resected melanoma, once the following criteria have been met:

- 1) Histopathologic confirmation of melanoma
- 2) Confirmation of adequate tumor content in resection specimen for DNA sequencing

Patients will receive Nivolumab at a flat dose of 480 mg as a 30-minutes (+/- 10 min.) i.v. infusion every 4 weeks (28 days).

5.2.1.2 Nivolumab plus neoantigen vaccine (NeoVax plus Montanide) / Ipilimumab Period

Patients will begin therapy with neoantigen vaccine (NeoVax plus Montanide) / Ipilimumab once the vaccine has been prepared and testing completed at week 12. Patients will receive Nivolumab at a flat dose of 480 mg as a 30 minutes (+/- 10 min.) i.v. infusion every 4 weeks (28 days). Nivolumab will be given 60 minutes (+/- 10 min) following local Ipilimumab administration.

If therapy with neoantigen vaccine (NeoVax plus Montanide) / Ipilimumab gets delayed, vaccination timepoints will be modified as follows:

Neoantigen vaccine (NeoVax plus Montanide) / Ipilimumab vaccination timepoints #2 (week 15), #3 (week 18), and #4 (week 21) will be moved accordingly so there is a window of three weeks (+/- 3 days) between each vaccination timepoint. If any of the vaccine administrations coincide with Nivolumab treatment, neoantigen vaccine (NeoVax plus Montanide) / local Ipilimumab will be administrated first and Nivolumab will be given 60 minutes (+/- 10 min) following local Ipilimumab administration.

5.2.1.3 Nivolumab Continuation Period

After neoantigen vaccine (NeoVax plus Montanide) / Ipilimumab treatment has been completed, patients with unresectable stage IIIB/C/D or IV melanoma will continue to receive Nivolumab alone at a flat dose of 480 mg as a 30 minutes (+/- 10 min.) i.v. infusion every 4 weeks (28 days), until disease recurrence or progression, unacceptable toxicity, or withdrawal of consent, for a maximum duration of up to 2 years from the first study treatment in the Run in Period. Participants with completely resected melanoma will receive nivolumab for a maximum period of one year (13 doses)

5.2.2 Neoantigen Vaccine (NeoVax + Montanide® ISA-51 VG)

5.2.2.1 Injections

5.2.3.1.1 Neoantigen Vaccine (NeoVax + Montanide® ISA-51 VG)

Each of the Neoantigen Vaccine syringes will be assigned to one of two extremities. At each immunization, each NeoVax plus Montanide syringe will be administered s.c. to the assigned extremity (i.e., NeoVax + Montanide A will be injected into left arm week 12, 15 etc.; NeoVax + Montanide B will be injected into right arm week 12, 15). For participants who have undergone a complete axillary lymph node dissection, alternative anatomical locations are the left and/or right thigh or left and/or right midriff. The arms or left and/or right midriff can also be used for participants who have undergone a complete inguinal/femoral lymph node dissection (or other contraindications that prevent injections to a particular extremity). The personalized neoantigen vaccine (peptide + poly-ICLC + Montanide® ISA-51 VG) should be administered within 6 hours after preparing the peptide + poly-ICLC + Montanide® ISA-51 VG mixture, and injection sites may be shifted in order to avoid administering injections to areas with evidence of persistent local reaction.

NOTE: If emulsion of either pool A or pool B or both pools A and B is unsuccessful after two attempts, the vaccine will be prepared without Montanide (please see section 8.6.3).

5.2.3.1.2 Ipilimumab

Within 30 minutes (+/- 10 min) following NeoVax plus Montanide administration, Ipilimumab will be injected within 1 cm of each neoantigen vaccine administration.

5.2.2.2 Treatment window

Neoantigen vaccine (NeoVax plus Montanide) and Ipilimumab may be administered within 3 days of the scheduled administration date. (See Section 10; Study Calendar).

Days will not be counted continuously on protocol therapy. If a toxicity results in a hold of study vaccine and nivolumab administration, counting of days will hold until treatment resumes. (e.g. should patient not be able to receive his/her second vaccine at Week 15 due to a toxicity, counting is held; if the toxicity has resolved a week later, the administration of that second vaccine becomes the participant's new Week 15) Following a dose delay, those day's

assessments should be repeated in order to restart participant's vaccinations.

5.2.2.3 Observation post vaccination

Participants should be observed in the clinic for at least 60 minutes after the last of the 4 injections and vital signs should be checked at 30 minutes (+/- 10 min) and 60 minutes (+/- 10 min) after the last injection for each clinic visit. Monitoring for immediate adverse events should include attention to possible injection site reaction or a systemic reaction. In the absence of the occurrence of an adverse event, participants will be discharged from the outpatient clinic at DFCI.

5.3 Pretreatment criteria

Preparation of the final Nivolumab, Ipilimumab, and/or Neoantigen vaccine product will begin upon confirmation that the participant is medically cleared to undergo treatment (confirmed arrival in the clinic, stable vital signs, no new acute medical issues or laboratory abnormalities potentially interfering with vaccine or Nivolumab administration).

5.3.1 Day 1

Laboratory parameters must be reviewed prior to administration of the study agents. No specific prophylactic or supportive care is necessary prior to administration of the study agents. Participants who have developed flu-like symptoms after NeoVax plus Montanide that are controlled with acetaminophen or non-steroidal anti-inflammatory drugs during previous treatments may be pre-treated with acetaminophen (650 mg PO) or ibuprofen (400-600mg PO) as per the investigator's discretion.

5.3.2 Subsequent treatment days

The following must be reviewed and confirmed within three days prior to subsequent treatment administrations:

1. Stable vital signs
2. ECOG performance status
3. No new acute medical issues that would require a dose hold or delay as noted in dose modification section 6.3

No specific prophylactic or supportive care is necessary prior to administration of the study agents.

5.4 Dose schema and staggering of participants

5.4.1 DLT and expansion cohorts

Adverse events classified as dose-limiting toxicities (DLT) and the assessment time for DLTs are summarized in Section 5.5. Five patients will be treated with NeoVax plus Montanide plus local Ipilimumab plus Nivolumab (starting at week 12) for the initial safety evaluation (Cohort 1). We have chosen dose escalation cohorts of 5 patients, rather than a more traditional 3+3 design,

because the determination of whether to treat at a different dose in this trial is made over a longer period of time due to the time required for vaccine preparation and the extended period for safety evaluation. These larger cohort sizes help us avoid having to pause and then restart enrollment to a dosing cohort several months later.

If none or only 1 patient in Cohort 1 experiences a dose limiting toxicity (DLT) during the first 7 weeks of treatment (NeoVax plus Montanide plus local Ipilimumab plus Nivolumab) of Cohort 1, 5 patients will be treated as Cohort 2 Dose Level 2. If two or more patients in Cohort 1 experience a DLT during the first 7 weeks of treatment, then 5 patients will be treated as Cohort 2, Dose Level -1.

If none or only 1 patient experiences a DLT on Cohort 2 Dose Level 2, then Dose Level 2 will be the maximum tolerated dose (MTD) and an additional 10 patients will be treated at that dose level (Cohort 3, Dose Level 2) to increase the likelihood of detecting serious toxicities, to complete biologic correlative endpoints and to gain preliminary experience with clinical tumor activity. If two or more patients in Cohort 2 Dose Level 2 experience dose limiting toxicity (DLT), then Dose Level 1 will be the MTD and an additional 10 patients will be treated in an expansion cohort at this dose (Cohort 3 Dose Level 1).

If none or only 1 patient experiences a DLT on Cohort 2 Dose Level -1, then Dose Level-1 will be the maximum tolerated dose (MTD) and an additional 10 patients will be treated in an expansion cohort at that dose level (Cohort 3 Dose Level-1). If two or more patients in Cohort 2 Dose Level -1 experience dose limiting toxicity (DLT), then the study will be stopped.

Dose Escalation schedule		
	Dose Level	Dose of Ipilimumab
	-1	1.25 mg (0.25 mL)
Starting Dose -->	1	2.5 mg (0.5 mL)
	2	5 mg (1.0 mL)

5.4.2 Staggering of patients

The first three patients will be enrolled in a staggered fashion: Patients 2 and 3 will not start treatment until the previous patient has completed 4 weeks after the first dose of the NeoVax vaccine.

5.4.3 Definition of evaluable participants

All participants receiving at least one dose of Nivolumab will be evaluable for toxicity. Participants will be evaluable for immunologic activity if they have received all vaccinations during the priming phase and the first boost vaccination.

Participants with unresectable and measurable disease who have received at least one dose of study vaccine therapy will be considered evaluable for determination of tumor response.

A minimum of 2 vaccinations and absence of DLTs are required for a participant to complete the

6-week DLT observation period successfully.

5.5 Definition of Dose-Limiting Toxicity

Dose-limiting toxicity (DLT) is based on the CTEP Active Version (version 5.0) of the NCI Common Terminology Criteria for Adverse Events (CTCAE). DLT refers to toxicities experienced within 42 days (6 weeks of Neoantigen Vaccine treatment initiation i.e. 2 vaccinations “DLT window”). If treatment has to be delayed because of a toxicity that does not fulfill the criteria of a DLT, the DLT window should be extended by that time period of delay. A DLT will be defined as follows:

1. Grade 3 or 4 toxicity that is definitely, probably, or possibly related to the administration of vaccine, excluding:
 - Transient (\leq 72 hours) flu-like symptoms
 - Grade 3 nausea, vomiting, diarrhea, or constipation that returns to grade 2 (or lower) level within 48 hours
 - Any grade 3 rash that resolves to grade 2 or grade 1 within \leq 14 days
 - Any grade 3 endocrine abnormality that is corrected with hormonal therapy within 4 weeks
2. Grade 3 or 4 abnormal laboratory value that is definitely, probably, or possibly related to the administration of vaccine if it persists for more than 7 days, or requires hospitalization or medical intervention excluding:
 - Any grade 3 electrolyte abnormality:
 - lasts \leq 72 hours,
 - is not clinically complicated,
 - and resolves spontaneously or responds to conventional medical intervention
3. Any grade 3 or grade 4 toxicity that is considered, in the opinion of the Principal Investigator, to be dose-limiting.
4. Any death related to study treatment.

Management and dose modifications associated with the above adverse events are outlined in Section 6 (Expected Toxicities and Dosing Delays/Dose Modifications).

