6.3.2 NeoVax plus Montanide

6.3.2.1 If a participant develops grade 3 toxicity attributable to the vaccine, additional treatment will be withheld until the toxicity has resolved or improved to grade 1. If the toxicity constitutes a DLT as defined in 5.6, the participant will be removed from the study. If the toxicity does not fulfill the criteria of a DLT, the next vaccine administration may be delayed for a maximum duration of 14 days. If vaccine dosing has to be delayed more than 2 times because of an attributable toxicity that is not considered a DLT, the participant will be removed from the study

6.3.2.2 If a participant develops grade 4 toxicity attributable to the vaccine s/he will be removed from treatment

6.3.2.3 If two or more grade 4 or greater toxicities attributable to the vaccine are observed, the trial will be suspended to investigate the causes of these (unexpected) toxicities

6.3.2.4 Vaccine dosing may be delayed in the event of unrelated adverse events if it is felt to be in the medical best interest of the patient following discussion by the treating investigator with the study Principal Investigator or designee. Vaccine dosing may be resumed once the treating investigator deems it is medically safe to do so following discussion with the study Principal Investigator or designee as long as the participant has not developed progressive disease

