Blood draw for immune response monitoring			X ^d	X ^d		X ^d			X ^d
Neoantigen vaccine administration		X				X		X	
Ipilimumab administration		X				X		X	
Vaccine site skin biopsy						X ^c			

a Leukapheresis procedure will be performed at the following timepoints:

- within 14 days before first vaccination timepoint #1
- within 7 days before vaccination timepoint #4

At each Leukapheresis collection timepoint 2x10 mL EDTA tubes will be collected. These tubes should be dropped off at the IAL upon collection

NOTE: If Leukapheresis cannot be performed a total of 200mL of blood should be drawn. If starting of vaccine administration gets delayed, week 20 leukapheresis will be collected before vaccination timepoint #4.

b Tumor biopsies will be collected at the following timepoints:

- within two weeks before starting the neoantigen vaccine Dose #1
- within two weeks prior to neoantigen vaccine Dose #4
- at the time of progression

At a minimum, 5 core biopsies or a surgical tumor specimen of 100mm³ will be obtained. Skin punch biopsies of a skin lesion are also allowed

c Expected neoantigen vaccine administration timepoints (see below). If there is a delay in vaccine preparation, Dose #1 should be administered as soon as the neoantigen vaccine is available. Doses #2, #3, and #4 should be scheduled every 3 weeks after Dose #1:

- neoantigen vaccine Dose #1: Week 12
- neoantigen vaccine Dose #2: Week 15
- neoantigen vaccine Dose #3: Week 18
- neoantigen vaccine Dose #4: Week 21.

If neoantigen vaccine administration coincides with nivolumab administration, neoantigen vaccine + Ipilimumab will be administered before Nivolumab

d Unless otherwise specified, 80 ml of blood will be drawn for immune monitoring. Blood collections will be performed at the following timepoints:

- one week (+/- 3 days) after neoantigen vaccine Dose #1
- before neoantigen vaccine Dose #2
- before neoantigen vaccine Dose #3
- within 3 weeks (+/- 3 days) after neoantigen vaccine Dose #4
- before each nivolumab administration during the post vaccination period

e Skin biopsies near vaccine injection sites (two 5 mm punch biopsies) should be performed at the following timepoints:

- prior to neoantigen vaccine Dose #3,
- between 48-72 hours after neoantigen vaccine Dose #3

Additionally, if a different vaccine site appears to clinically have a higher degree of inflammation, additional punch biopsy (two 5mm) of that site may be taken.

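### The DLT window is extended only for toxicity delays, so a patient whose second vaccination is late for another reason can count as DLT-free with shortened follow-up

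*Protocol*

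**What the plan says.** Protocol 5.5 defines the window: "DLT refers to toxicities experienced within 42 days (6 weeks of Neoantigen Vaccine treatment initiation i.e. 2 vaccinations". It gives one ground for lengthening it, treatment that is "delayed because of a toxicity that does not fulfill the criteria of a DLT, the DLT window should be extended by that time period". The study-day clock follows the same logic in section 5 ("If a toxicity results in a hold of study vaccine administration, counting of days will hold until treatment resumes") and again in 5.2.2.2.

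Delays for other reasons are allowed. Protocol 6.3.2.4 states: "Vaccine dosing may be delayed in the event of unrelated adverse events", and sets no maximum there. The 14-day limit in 6.3.2.1 concerns toxicity attributable to the vaccine. Section 6.4 has a general 6-week limit, and 6.5 allows exceptions, including one for non-drug reasons. Section 5.2.1.2 moves later vaccination dates after a delay but does not mention the DLT window.

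The test for passing is in 5.4.3: "A minimum of 2 vaccinations and absence of DLTs are required for a participant to complete the" 6-week observation period. Section 13.1 and the SAP repeat the test with a 7-week period. None of the three states a minimum time under observation after dose 2.

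The window length is not consistent. Protocol 5.4.3 and 5.5 use 6 weeks (42 days), while 5.4.1 and 13.1 use 7 weeks for the cohort decision, although 13.1 refers to 5.5 for the assessment time. The SAP uses both.

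**The concern.** By extending the window for toxicity delays, 5.5 accepts that a late second dose needs its observation time restored. Restricting this to one cause means that two patients with the same delay can get different windows.

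The DLT rate is the primary endpoint, and a cohort of five clears on 0 or 1 DLT, so a single event can decide it. A patient with little follow-up after dose 2 enters that count, and the denominator of the DLT rate, as a fully observed DLT-free patient. Shorter observation can only remove events, so the error runs in one direction: towards a lower DLT rate and easier clearance.

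**Working it through.** **Inputs.**
- Window W: 42 days from dose 1 (5.5), or 49 days (7 weeks in 5.4.1, 13.1 and the SAP).
- Dose interval: "Doses #2, #3, and #4 should be scheduled every 3 weeks after Dose #1" (section 10), so dose 2 is due on day 21.
- Allowance: "Neoantigen vaccine (NeoVax plus Montanide) and Ipilimumab may be administered within 3 days of the scheduled administration date" (5.2.2.2).
- Clearing rule: 0 or 1 DLT in 5 (5.4.1, 13.1).

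**The plan's own figures.** Two intervals of 21 days give the 42-day window. P(0 or 1 DLT in 5) = (1−p)^5 + 5p(1−p)^4 gives 91.9, 73.7, 52.8, 33.7, 18.8 and 8.7% at p = 10 to 60%. These match the table in 13.1 (92, 74, 53, 34, 19, 9).

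**Observation after dose 2.** With dose 2 delayed by d days and no extension, the days left are W − (21 + d).

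| Delay d (days) | 42-day text | 49-day text |
|---|---|---|
| 0 | 21 | 28 |
| 3 (within allowance) | 18 | 25 |
| 4 | 17 | 24 |
| 7 | 14 | 21 |
| 14 | 7 | 14 |
| 18 | 3 | 10 |
| 21 | 0 | 7 |

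The ±3-day allowance alone gives 18 to 24 days on the 42-day text, so 18 to 20 days is ordinary scheduling. The affected range starts at d = 4. Beyond d = 21, dose 2 falls outside a 42-day window and the two-vaccination condition is not met within it.

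**Effect on clearing a cohort (illustration, 42-day text).** Assumptions: total DLT risk p is split equally between the two doses; onset is uniform over the 21 days after each dose; the delay itself adds no risk.
- Risk per dose: q = 1 − √(1−p). At p = 0.30, q = 0.1633.
- Observable risk of the late patient: p* = 1 − (1−q)(1 − q(21−d)/21).
- The other four patients: P(0 DLT) = 0.7^4 = 0.2401 and P(1 DLT) = 4 × 0.3 × 0.7^3 = 0.4116.
- P(clear) = 0.2401 + 0.4116(1 − p*) = 0.6517 − 0.4116p*.

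| One late patient, p = 0.30 | p* | P(clear) |
|---|---|---|
| d = 0 | 0.300 | 0.528 |
| d = 7 | 0.254 | 0.547 |
| d = 18 | 0.183 | 0.576 |

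At p = 0.40, q = 0.2254 and P(clear) = 0.4752 − 0.3456p*. The results are 0.337 with no delay, 0.357 at d = 7 (p* = 0.342) and 0.389 at d = 18 (p* = 0.250).

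**Sensitivity to the onset assumption.** Under a constant hazard, with 50% to 100% of the cumulative hazard falling after dose 2, one patient 7 days late at p = 0.30 gives 0.546 to 0.565. One patient 21 days late gives 0.584 to 0.652.

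**On the 49-day text.** Under the same uniform-onset model, a 7-day delay leaves the full 21 days and changes nothing. An 18-day delay leaves 10 days, so p* = 1 − 0.8367 × (1 − 0.1633 × 10/21) = 0.228 and P(clear) = 0.6517 − 0.4116 × 0.228 = 0.558. This leaves out any risk from dose 3, which is scheduled for day 42.

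**The case against.** **The extension may already cover unrelated adverse events.** Section 5.5 speaks of a toxicity without requiring it to be related. Elsewhere, including in the DLT definition itself and in 6.3.2.1, the protocol adds relatedness when it means it. An unrelated event that holds the vaccine could then be a toxicity that is not a DLT. Against this, 6.3.2 treats toxicity attributable to the vaccine and unrelated adverse events as separate matters. The term is not defined, so a reader who infers that every unrelated-event delay is excluded goes further than the text. This part of the objection stands. Delays not caused by any adverse event are outside the extension on either reading.

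**The cohort decision is written in weeks, and the number is 7.** A reader might take 0 to 20 days against 21 as the settled loss. That holds only on the 42-day text and counts ordinary scheduling as loss. On the 7-week text a 21-day delay still leaves 7 days. The objection changes the size of the gap but does not remove it.

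**Delay is not unlimited.** Section 6.3.2.4 sets no maximum, but the 6-week limit in 6.4 applies, with the exceptions in 6.5. Since 6 weeks is longer than 21 days, the limit does not prevent the loss shown above.

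**The effect is small unless the delay is long.** This stands. A 7-day delay in one patient moves clearance by about 2 percentage points at 30% risk, and 18 days is close to the worst case.

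**Escalation is over.** This also stands. The SAP's modified design says that accrual stopped at the end of escalation and that expansion did not begin, so editing 5.5 cannot change any decision already taken.

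**Conclusion.** The gap holds in limited form. A second vaccination that is late for a non-toxicity reason shortens DLT observation by the length of the delay, and nothing in the pass condition catches it. For delays outside the ±3-day allowance and up to 21 days, 17 down to 0 days remain after dose 2 on the 42-day text (nominal 21), or 24 down to 7 on the 7-week text (nominal 28).

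The direction is certain: fewer DLTs. The size is not, because the documents give neither an onset distribution nor a frequency for such delays. Under the stated assumptions and the 42-day text at 30% risk, one late patient raises the chance of clearing a cohort from 53% to 55% (7 days) or 58% (18 days).

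A reader might infer that the declared MTD or the observed DLT rate is wrong. The documents do not support that, since nothing in them shows that any patient had such a delay. The point is an unchecked route to under-counting in the primary endpoint.

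**What to change.** 1. Reconcile the 6-week and 7-week windows across protocol 5.4.1, 5.4.3, 5.5, 13.1 and the SAP.
2. State once that the window is extended by the length of any delay of the second vaccination, whatever its cause, so that each patient keeps the on-schedule observation time after dose 2. The end of the window should not be tied to the third vaccination, because the ±3-day allowance lets dose 3 fall 18 to 20 days after dose 2.
3. In the SAP's DLT-rate analysis, check each patient's dose 2 date against schedule, re-apply the extended window to the recorded adverse events, report the DLT rate on that basis, and flag any patient whose status changes.

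The cost is a sentence in 5.5, a matching one in the SAP and a short data check. Protocol section 6 already collects adverse events from the first nivolumab dose to the final visit. The adverse-event variables listed in the SAP include a DLT flag but no onset date, so onset and dosing dates would need to be added to that list. The downside is that a late event may newly count as a DLT and, if the design is used again, a dose decision may wait by the length of the delay.
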